## Data Collection Procedures

**Overview and timeline for the proposed data collection:** In the proposed study, a total of at least 380 youth will be recruited and baseline assessed for the study. We anticipate that approximately 10% of these will fail to complete the study, resulting in a sample of at least 342 youth with complete data and an intent-to-treat analysis strategy which will include all 380 youth. We will conduct baseline assessments and follow-up assessments at treatment completion (1 month), and at 3 month post-baseline.

**Assessments:** The *baseline assessment* primarily measures youth risk factors, as well as past and current substance use, and will consist of an in-person interview including questionnaires with the youth.

The *treatment completion (1-month), and 3-month assessments* are aimed at assessing short and longer term outcomes and will consist of two components: (a) an in-person interview and questionnaires with the youth, and (b) usability and satisfaction ratings for the Qlarity app. Because every participant has unique needs, we have standardized guidelines that allow for minor modifications to our procedures when needed. For example, staff will read aloud questionnaires for participants who are nonreaders, and computer-assisted questionnaires will be available in hardcopy format. We will travel to participant residences or other locations to conduct the interviews as needed.

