**Main-effects analyses.** Tests of the general effectiveness of the Qlarity app within this three-panel (pretest, 1- month, and 3-month follow-up) randomized trial requires an analysis that accounts for the dependence of multiple assessments nested within participants that were assigned to conditions. Thus, we will test most of our research hypotheses with random effects growth models within the hierarchical and structural equation modeling (SEM) frameworks with individual variability in change in study outcomes from pretest to 3-months nested within individuals. Following Singer and Willet when constructing the longitudinal model, we will (a) examine empirical growth plots; (b) fit an unconditional means model; (c) fit an unconditional linear growth model; (d) fit unconditional non-linear models; and (e) compare models of longitudinal change from the previous two steps using the Akaike Information Criterion. Individual variability change in the outcomes from baseline to the 3-month follow-up assessment will be modeled as a function of intervention condition. Intervention condition by time interactions will test whether groups differ on individual trajectories over the course of the study period. We will also use logistic regression models reporting odds ratios (OR) to test for differential rates of abstinence at the 3-month follow-up assessments with intervention condition a two-level predictor.

**Moderator effects.** Moderating effects of demographics (gender and minority status) and number of baseline offenses will be explored by adding the moderator to the random effects growth models described above. The multiplicative interaction term between the participant level moderators constitute a three-way cross-level interaction with time in the growth models and addresses whether the level of the baseline moderator impacted the magnitude of intervention condition on change in the outcome. All significant cross-level interactions will be probed by computing sample-estimated intercepts and slopes of the trajectories of the outcomes at conditional levels of the moderator, separately, within the Qlarity and usual care group (i.e., simple trajectories) using methods described by Curran (Curran, Bauer et al. 2006).

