**Mediation effects.** Growth-curve models implemented in an SEM framework will be used to explore whether observed condition effects on tobacco, alcohol, and drug use are mediated by adolescent attitudes and mindfulness. Following Preacher et al., models will be constructed by individually fitting growth models for mediators and outcomes using the growth curve model-building sequence described above to develop the best longitudinal change model. Then mediator and outcome growth curves will be combined in a single model. We will test whether (a) condition predicts change in each mediator, (b) condition predicts change in each outcome, (c) mediator change predicts outcome change, and (d) the condition effect on the outcome is significantly weaker when controlling for level or change in the mediator. Significance of indirect effects will be tested using bias-corrected bootstrapped confidence intervals.

**Process analyses.** A critical element to the program evaluation is the acceptability of the intervention to the target population, which will be assessed via rate of attrition, level of program

use, and degree of program satisfaction. Dose-response analyses will be conducted to examine the degree to which treatment engagement and retention (e.g., frequency and duration of app use, number of modules completed) predict change in the outcome measures at the post-intervention and follow-up assessments. Canonical correlation analyses will be used to examine the association between the dosage measures and outcome measures within the Qlarity condition. We will also test the hypothesis that those participants who report greater satisfaction with the intervention will have greater improvement in baseline-post scores using residual gain score analyses. Lastly, treating participant satisfaction as a process variable, we will examine the correlations between the satisfaction ratings and the amount of treatment engagement/retention.

**Missing data.** Missing data in outcome measures may result from dropout or item non-response. The mixed- growth models described above make use of maximum likelihood estimates and allow for use of all available outcome data from all assessments, reducing bias and increasing power. In general, maximum likelihood procedures, as well as imputation methods, will be used as they can provide unbiased estimates even in instances of substantial attrition. Multiple imputation procedures will follow best-practice recommendations.

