**Power considerations.** The assumptions for the power estimates include a sample size of 380 participants, Type II error rate of 20% ( $\beta = .20$ ) and a 2-tailed alpha = .05. Power estimates for multilevel growth models require assumptions that are not easily established in longitudinal studies (e.g., complete data, homogeneous random-effects covariance structures within conditions). Thus we rely on the fact that power for multilevel growth models has been shown to surpass that of the mixed-model ANCOVA. The proposed growth models, then, will detect smaller differences between conditions than the ANCOVA models on which power estimates were based. Allowing for intent-to-treat analyses that makes use of all available data using missing data techniques described above and a pretest covariate  $r^2 = .25$ , there is sufficient power to detect main effects for condition of Cohen's  $d = .25$  (small effect size) and detect condition by moderator effects of  $d = .35$  (small to medium effect). The smallest subsample expected for decomposition of significant moderating effects is approximately 150 minority participants (75 per condition) which will provide sufficient power ( $>.80$ ) to detect condition effects of  $d = .40$  (medium effect). The study is also powered to detect small to medium between condition effect size differences (ORs = 2.05 – 2.25) for the logistic regression models predicting an estimated 15-20% substance use abstinence rates at follow-up. Using mediation effect size guidelines from Kenny for a model containing a dichotomous independent variable and a continuous mediator, effect sizes of .02, .15, and .40 derived from the product of  $d$  and  $r$ , represent small, medium, and large effect sizes respectively. Assuming small to moderate effects for the indirect pathway ( $r = .20$ ), the proposed sample size has sufficient power ( $>.94$ ) to detect small effect sizes or greater ( $dr = .04$ ) for tests of mediation. Process analyses involving correlation coefficients will have adequate power to detect small to medium effects ( $r = .20$ ).

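### The 80% power for d = .25 is an ANCOVA figure on all 380 youth; it is not shown for the planned condition-by-time growth test, which has about 70% in the simplest case

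*Combined protocol and SAP*

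**What the plan says.** Data Analysis, Power considerations, sets two-tailed alpha .05, beta .20 and a pretest r² of .25, and states "The assumptions for the power estimates include a sample size of 380 participants". It claims enough power for a condition main effect of d = .25. It acknowledges that growth-model power needs assumptions that are hard to establish, and continues: "Thus we rely on the fact that power for multilevel growth models has been shown to surpass that of the mixed-model ANCOVA". It concludes: "The proposed growth models, then, will detect smaller differences between conditions than the ANCOVA models on which power estimates were based".

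Data Analysis, Main-effects analyses, fits random effects growth models to the pretest, 1-month and 3-month waves. The form of time is chosen by fitting unconditional linear and non-linear models and then to "compare models of longitudinal change from the previous two steps using the Akaike Information Criterion". The test of the intervention is: "Intervention condition by time interactions will test whether groups differ on individual trajectories over the course of the study period". Separately, logistic regression is used "to test for differential rates of abstinence at the 3-month follow-up assessments".

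On loss, Data Collection Procedures says: "We anticipate that approximately 10% of these will fail to complete the study", leaving at least 342 with complete data. Data Analysis, Missing data, relies on maximum likelihood models that "allow for use of all available outcome data from all assessments, reducing bias and increasing power".

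**The concern.** The stated power belongs to one test and the plan runs another. ANCOVA gains precision by conditioning on the pretest. A condition-by-time test whose baseline means are free by arm does not get that gain, because it estimates a baseline difference that randomisation already makes zero in expectation.

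The r² of .25 fixes only one pretest-posttest correlation. Growth-model power also depends on the other two correlations, the shape of the effect over time, the fitted covariance and the handling of baseline. The plan states none of these.

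If the carry-over fails, the trial has less than its stated chance of detecting the effect it was sized for. The feasibility benchmark that requires significantly greater decreases in substance use under Qlarity inherits the shortfall.

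**Working it through.** **Inputs from the plan.** 190 per arm; two-sided .05; d = .25; r² = .25, so r = .5; assessments at 0, 1 and 3 months; 10% loss, leaving 171 per arm.

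**Assumptions not in the plan.** d = .25 is the effect at month 3; variances are equal (total variance 1); the baseline to month-3 correlation is .5. The other correlations and the effect shape are varied below.

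**1. Reproduce the stated 80%.** For ANCOVA, SE = √(1 − r²) × √(2/n), and power ≈ Φ(d/SE − 1.96).
- n = 190: SE = .8660 × .1026 = .0889; .25/.0889 = 2.81; power .803 (noncentral t .801).
- n = 171: SE = .8660 × .1081 = .0937; .25/.0937 = 2.67; power .761 (noncentral t .759).
- n = 190 without the covariate: .683.

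The stated figure is therefore the pretest-adjusted one on all 380. The minimum detectable d is .25 with 380 and .26 with 342.

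**2. Planned test, simplest case.** Baseline free by arm, uniform correlation ρ = .5, effect linear in time. With times 0, 1, 3 the mean is 4/3 and Σ(t − t̄)² = 16/9 + 1/9 + 25/9 = 4.667. The variance of the slope difference is 2(1 − ρ)/(4.667 n).
- n = 190: variance = 1/886.7, SE = .0336. The slope difference is .25/3 = .0833; .0833/.0336 = 2.48; power .699. Minimum detectable d = 3 × .0336 × 2.80 = .28.
- n = 171, completers only: variance = 1/798, SE = .0354; ratio 2.35; power .653.
- 10% loss, maximum likelihood on the remaining waves (generalised least squares information): .662 if the lost youth give baseline only, .663 if they miss only month 3.

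Maximum likelihood therefore recovers little. A youth with no follow-up carries almost no information on the condition effect.

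**3. Other uniform correlations (380 complete, linear effect).**

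| ρ | Free-baseline growth test | ANCOVA |
|---|---|---|
| .3 | .555 | .724 |
| .4 | .620 | .758 |
| .5 | .699 | .803 |
| .6 | .792 | .861 |
| .7 | .893 | .927 |

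The growth test is below ANCOVA in every row.

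**4. Unequal correlations.** Baseline to month 3 is held at .5. Baseline to month 1 runs from .4 to .7 and month 1 to month 3 from .4 to .8 (63 patterns, N = 380). Visit means are modelled as linear in time except in the last row.

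| Test | Linear effect | Effect complete by month 1 |
|---|---|---|
| Free baseline, true covariance | .68–.91 | .22–.82 |
| Free baseline, random intercept and slope, equal residual variances | .65–.78 | not tabulated |
| Equal baseline means | .80–.92 | .40–.96 |
| Conditioned on pretest, visit categorical, 3-month contrast | .80 throughout | .80 throughout |

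At uniform .5 with the effect complete by month 1, the free-baseline linear slope has .566, a 2-df time form .71, and pretest versus the mean of the follow-ups .80. The grid is an assumption, so the share of patterns above 80% is not a probability.

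**The case against.** The strongest reply is that the plan is silent on baseline handling and that its power text names a pretest covariate, so equal baseline means are a possible reading. Under that reading and a linear effect, power is .80 to .92 across the grid and never below ANCOVA. This stands as a statement about that reading. However, the Main-effects text does not state the constraint, and the Moderator effects text computes intercepts and slopes separately within each group. At uniform .5 the constrained model only equals ANCOVA (.803), with .76 to .77 after 10% loss. It can also fall to .40 if a linear slope is fitted to an effect complete by month 1.

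Other points carry some weight:
- The plan allows non-linear time forms, so the lowest figures describe a test that may not be run. Selecting among unconditional models, though, does not fix the condition contrast in advance.
- Placing d = .25 at month 3 is an assumption. A pretest-adjusted mean of both follow-ups with a constant effect would have about .93 at uniform .5, but that is not the condition-by-time test.
- The claim about growth models may once have carried a citation, and the plan's overview points to a fuller power section. A general citation could not make the claim a bound where these calculations contradict it.
- The 3-month contrast is one choice among several, and its constant .80 follows directly from fixing the baseline to month-3 correlation at .5. Stating the growth model's own power would also repair the defect.

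**Conclusion.** The power statement is wrong as written. The 80% reproduces only for an ANCOVA with outcomes from all 380, and the claim that growth models must do better is not a valid floor. In the simplest case (free baseline, uniform .5, linear effect) the planned test misses a true d = .25 about 30% of the time, or about 34% with the expected loss, rather than 20%; the minimum detectable d at N = 380 is .28 instead of .25. These are one scenario. Power exceeds 80% when the follow-ups are strongly correlated and the fitted covariance reflects it.

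Two conclusions do not depend on the scenario: no growth-model power is given, and ANCOVA itself has about 76% with 342. Type I error and the logistic abstinence test are unaffected. This should be fixed before analysis.

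**What to change.** For continuous outcomes, make the main-effect test the 3-month condition contrast from a model with the 1- and 3-month values as outcomes, visit as a category, condition-by-visit, pretest, pretest-by-visit and an unstructured covariance. Equivalently, use all three waves as outcomes with baseline means constrained equal across arms and visit still categorical. Month 3 is suggested because the abstinence test is already there; if the sponsor prefers the average of both follow-ups, name it and give its power. Keep the growth model as secondary, with equal baseline means.

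Delete the two sentences that say growth models outperform ANCOVA. Restate power for d = .25 as about .80 with complete data and about .76 with 342 completers (minimum detectable d about .26). If the growth model stays the main test, give its power with the assumed wave correlations, effect shape, residual structure, baseline handling and 10% loss.

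The cost is SAP wording and a slightly less favourable stated power. A 3-month contrast also gives up the growth model's extra power when the effect is linear and the follow-ups are strongly correlated. No new data or participants are needed, and randomisation justifies the equal-baseline constraint.

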**Focus Groups and Usability Testing:** Twenty high-risk adolescents will be recruited to participate as test users in the development phase to give us initial reactions to mockup of modules, and a subgroup of 10 of these participants will be recruited to participate in preliminary usability testing of the modules. Feedback from usability testing will be used to inform adaptations to the app. The prototype app will then be evaluated in an efficacy trial with 380 additional high-risk adolescents. The primary outcomes of the evaluation-testing phase will be changes in adolescent substance use attitudes and behaviors and emotion regulation measured at three time points: baseline, 4 weeks post- baseline (end of treatment), and three months post-baseline. The proposed efficacy trial will evaluate the extent that the Qlarity app influences positive behavior change and will provide power estimates for later larger scale evaluation.

**Efficacy Trial:** Based on our power calculations, we will recruit 380 adolescents who are involved in the juvenile justice system. We have a long history of cooperation with the DHS and have well-established recruitment procedures. Eligible adolescents and their consenting parents will be recruited on a continual basis and will be included in the study for 3 months post-baseline. The participants will be randomly and equally assigned to the Qlarity condition ( $n = 190$ ) or the DC standard treatment condition ( $n = 190$ ) following adolescent assent and parent consent. Given that all youth will be involved in the juvenile justice system, we will assess all services offered and accessed by youth in both conditions.

Based on our prior experience, we expect many of the youth to be under orders to be participating in urine screening or other intervention services through DHS. Data from our current and prior studies with this population suggest that despite receiving random urine screens as part of their probationary status, 90% of youth are involved in ongoing alcohol, tobacco or other drug use (79% alcohol; 68% tobacco; 81% marijuana, and 53% other drug; 90% positive for one or more substance) at the time of referral. We will track additional services, including mandated urine screens, via official DHS reports and using a services utilization measure at each follow-up time point.

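### The claimed power for condition-by-moderator effects of d = .35 does not hold for gender or minority status: power is about one half, and the detectable difference is about .50

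*Combined protocol and SAP*

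**What the plan says.** The Power considerations paragraph of the Data Analysis section sets out its basis: "The assumptions for the power estimates include a sample size of 380 participants", a "Type II error rate of 20"%, two-tailed alpha of .05 and a pretest covariate r² of .25. ANCOVA is the model behind the estimates. The paragraph then claims sufficient power for a main effect of Cohen's d = .25 "and detect condition by moderator effects of $d = .35$ (small to medium effect"). The next sentence turns to subgroups: "The smallest subsample expected for decomposition of significant moderating effects is approximately 150 minority participants (75 per condition"), for whom power above .80 is claimed at d = .40. On the planned analysis the paragraph adds: "The proposed growth models, then, will detect smaller differences between conditions than the ANCOVA models on which power estimates were based".

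The Moderator effects paragraph names the moderators: "Moderating effects of demographics (gender and minority status) and number of baseline offenses will be explored". It describes the interaction as testing whether the size of the condition effect depends on the moderator. It then makes follow-up conditional on significance: "All significant cross-level interactions will be probed by computing sample-estimated intercepts and slopes".

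**The concern.** An interaction with a binary moderator is a difference between two subgroup effects, so it carries the sampling error of both. With four equal cells its standard error is twice that of the main effect. A design that just detects .25 as a main effect should therefore just detect about .50 as an interaction, not .35.

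The paragraph also seems to conflict with itself. It needs .40 for 80% power within the minority subgroup alone, yet claims .35 for a contrast that includes that subgroup's error plus the error of the other 230 youth.

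Subgroup trajectories are examined only after a significant interaction. If power is about one half, about half of true .35 differences by gender or minority status would never reach that step, while the plan tells its readers that power is sufficient.

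**Working it through.** **Inputs.** From Power considerations: N = 380, two-sided alpha .05, 80% power, r² = .25, and 150 minority participants (75 per condition), which leaves 230 others (115 per condition). From the Efficacy Trial paragraph: 190 per condition. The gender split is not given; 50/50 is assumed, which is the most favourable case.

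**Formula.** SE = √(1 − r²) × √(sum of 1/n over cells), with √.75 = .866. Power comes from the noncentral t. The detectable effect at 80% power is about (1.96 + .84) × SE; the table uses the t-based version.

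**Step 1: reproduce the plan's other figures.**
- Main effect: SE = .866 × √(2/190) = .0889. Power at .25 is .801.
- Minority subgroup: SE = .866 × √(2/75) = .1414. Power at .40 is .802.

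Both stated figures sit at the 80% threshold, so the method and inputs are recovered.

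**Step 2: the interaction, as a difference between two condition effects.**

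| Split | SE | Power at .35 | Detectable at 80% |
|---|---|---|---|
| 50/50 (95 in each of 4 cells; assumed) | .866 × √(4/95) = .1777 | .502 | .499 |
| 150/230 (75, 75, 115, 115) | .866 × √(2/75 + 2/115) = .1818 | .484 | .511 |

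ANCOVA simulations of 20,000 runs per split gave .50 to .51 and .49. A 70/30 gender split (assumed) gives power .44. With the 342 completers expected under Data Collection Procedures, power is .46 (50/50) and about .45 (minority split), and the detectable differences are about .53 and .54.

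**Step 3: internal comparison.** In the minority subgroup alone (SE .1414), power at .35 is .69. The interaction has a larger SE (.1818), so its power at .35 must be lower.

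**Step 4: what .35 does match.** The condition effect within half the sample (95 per arm) has SE = .866 × √(2/95) = .1257 and a detectable effect of .354, which is also .25 × √2. That is a simple effect, not an interaction. That the plan's figure arose this way is an inference from the arithmetic.

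**Step 5: what would rescue .35.** The SE would have to be about .125, which is 30% (50/50) or 31% (150/230) below the values in the table. At N = 380 this needs r² of about .63 or .65. At r² = .25 it needs N of about 770 or 805.

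**Step 6: baseline offenses.** Treated as continuous and scaled per SD, the interaction SE is .866 × 2/√380 = .0889. The detectable effect is about .25 per SD, and power at .35 per SD is .98. The claim holds for this moderator.

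**The case against.** **The scale is not proven.** For two equal groups, Cohen's d equals 2f, so reproducing .25 and .40 cannot show which scale the interaction clause uses. If d means 2f there, f = .175 and power is about .98, so the sentence is true. This stands as a limit. But on that reading .35 stands for a .70 SD difference between subgroup effects, and the plan does not say so. The same sentence speaks of Cohen's d, and the Moderator effects paragraph describes the interaction as a change in the size of the condition effect. The 2f scale also gives about .25 as the 80% threshold, so it does not explain why .35 was chosen. The comparison in Step 3 likewise presumes the difference-of-effects scale.

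**Growth models may do better.** The plan says so but gives no size for the gain. Two checks under assumed correlations bear on this:
- For a linear effect expressed at 3 months, with a baseline-to-3-month correlation of .5, the growth-model SE was .95 to 1.15 times the ANCOVA SE, giving power of .39 to .55. This range does not bound the planned analysis, because non-linear models are also allowed.
- A more favourable case takes an equal effect at both follow-ups, tested on their mean, with r² = .25 for each. The residual variance is then (1 + ρ)/2 − .25, where ρ is the correlation between follow-ups. For ρ of .8, .5 and .3, power at .35 is .56, .67 and .77 (50/50), or .54, .65 and .75 (150/230). All remain below .80.

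**A fuller power section may exist.** The Statistical design and power overview refers to a separate Human Subjects section for details. No section with that title is in the supplied text. Power considerations may be that content; if it is not, a definition of d could lie there.

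**Moderation is exploratory.** This is true and lowers the weight of the point. It does not make an explicit power statement correct.

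**Conclusion.** The concern holds. On the natural reading of d, the stated .35 is not detectable at 80% power for gender or minority status. Power is about .50 for an even split and .48 for the plan's minority split, and the detectable differences are about .50 and .51. This rests on the plan's own N, alpha, r² and ANCOVA basis, on the difference-of-effects scale, and, for gender, on an assumed even split that is the best case. The conclusion does not extend to number of baseline offenses if analysed as continuous, and it would not apply if d were declared as 2f. The consequence is confined to a secondary power statement; the sample size and main-effect power are untouched. It should be corrected, because the plan asserts sufficient power that it does not have on that scale.

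**What to change.** - Define d for the interaction.
- Then take one of two routes. Either restate the binary-moderator figure as about .50 (.51 for minority status), with power of about .50 (.48) at .35; or relabel .35 as the condition effect detectable within a half-sample subgroup, and add the interaction figure beside it.
- Give number of baseline offenses its own figure, about .25 per SD if continuous.
- State the assumed gender split.
- If the growth model is relied on for extra power, state the size of the gain and the correlations assumed.
- Add that a non-significant interaction is not evidence of equal effects. The plan does not claim otherwise, so this is a safeguard.

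The cost is a few sentences of SAP wording and a less favourable stated figure, with no change to design or sample size.

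### The stated power above .94 for a mediated effect of dr = .04 does not follow from the plan's own d × r scale: at N = 380 it is about .55, or about .67 with a pretest covariate

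*Combined protocol and SAP*

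**What the plan says.** All the relevant statements are in the Data Analysis section of the combined protocol and SAP, apart from the dropout figure.

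- **Scale.** Under Power considerations, for a two-level condition and a continuous mediator, the plan gives "effect sizes of .02, .15, and .40 derived from the product of" d and r as its small, medium and large benchmarks.
- **Input.** "Assuming small to moderate effects for the indirect pathway ( $r = .20").
- **Claim.** The proposed sample "has sufficient power ( $>.94$ ) to detect small effect sizes or greater ( $dr = .04$ ) for tests of mediation".
- **Sample size and error rates.** "The assumptions for the power estimates include a sample size of 380 participants", with two-tailed alpha .05 and a general Type II error rate of 20%.
- **Main effect.** With a pretest covariate of r² = .25, "there is sufficient power to detect main effects for condition of Cohen's" d = .25.
- **Planned test.** Under Mediation effects: "Significance of indirect effects will be tested using bias-corrected bootstrapped confidence intervals".
- **Status.** The growth-curve models "will be used to explore whether observed condition effects on tobacco, alcohol, and drug use are mediated by adolescent attitudes and mindfulness".
- **Dropout.** Data Collection Procedures expects about 10% loss, "resulting in a sample of at least 342 youth with complete data", with all 380 in the intent-to-treat analysis.

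The plan does not state the value of d behind dr = .04, and it does not show the mediation power calculation.

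**The concern.** An indirect effect is detected only if both of its paths can be detected. On the d × r scale with r = .20, dr = .04 requires a condition effect of d = .20 on the mediator. The same paragraph puts the limit for a condition effect, at its general 80% power, at d = .25 with covariate adjustment. A product that depends on a smaller condition effect cannot plausibly have power above .94.

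The power figure tells a reader how much weight a non-significant mediation result can bear. As written, fewer than 6 in 100 trials (under 1 in 16) would miss a true effect of dr = .04. If the real miss rate is between 1 in 3 and nearly 1 in 2, a null result for attitudes or mindfulness could be misread as evidence against the mechanism on which the app is built. The plan also says that the trial will inform power estimates for a later, larger evaluation, so a wrong figure could be carried forward.

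**Working it through.** **Inputs.** N = 380 (190 per arm), two-sided alpha .05, r = .20, dr = .04 and covariate r² = .25, all from the plan. Hence d = .04 / .20 = .20. The plan gives the covariate for main effects. Whether it also applies to the mediator is not stated, so both versions are shown.

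**1. Check of method on the plan's own main effect.** Noncentrality = d / √(1 − r²) × √(n/2) = .25 / √.75 × √95 = 2.81. Two-sample noncentral t power is .801, which agrees with the plan's d = .25 at 80%.

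**2. Condition to mediator, d = .20.**
- Without covariate: .20 × √95 = 1.95, power .494.
- With covariate: .20 / √.75 × √95 = 2.25, power .612.

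**3. Mediator to outcome, r = .20.** Fisher z: atanh(.20) × √377 = 3.94, power .976.

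**4. Joint significance (both paths significant).** .494 × .976 = .482 without the covariate; about .60 with it.

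**5. Planned test.** The bias-corrected bootstrap was simulated in a single-mediator regression model with 1,000 resamples. The main runs had 2,000 to 4,000 trials (standard error about .01).

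| Effect (r = .20) | N | No covariate | Covariate r² = .25 |
|---|---|---|---|
| dr = .04 (d = .20) | 380 | about .55 (runs .54 to .57) | about .67 (runs .65 to .69) |
| dr = .04 (d = .20) | 342 | about .52 | about .63 |
| dr = .02 (d = .10) | 380 | about .21 | about .25 |

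At r = .20 and N = 380, 80% bootstrap power is reached at dr of about .055 (d = .275, power .806), or about .047 with the covariate (d = .235, power .796). At N = 342 the values are about .059 and .051.

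**6. Other readings of dr = .04, without / with covariate (joint significance).**
- Best possible split of .04 between d and r: .62 / .71.
- One-sided alpha: .61 / .72.
- 380 per arm, which the wording of the Statistical design and power overview could suggest: .79 / .89.
- Covariate r² needed on the mediator for joint power of .94: about .73, against .25 in the plan.

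None of these readings reaches .94 with the plan's inputs.

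**7. Where the stated figure does appear.** If both paths are correlations of .20, then .20 × .20 = .04 and joint power is .976² = .952, which fits a claim of above .94. But with 1:1 allocation a correlation of .20 with condition corresponds to d = 2(.20) / √(1 − .04) = .408. On the d × r scale the effect is then .408 × .20 = .082, about twice the stated .04. Bootstrap power at that effect is .97. At N = 342 the joint and bootstrap figures are .93 and .95.

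**The case against.** The arithmetic at d = .20 and r = .20 is not in dispute. The best opposing points are these.

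- **The calculation may be sound and only the label wrong.** The plan never states d, and r = .20 for the indirect pathway could mean both paths. This is a fair reading and the likely source of the figure. The sentence is still wrong as printed, because the scale it defines is d × r. The fix must allow for either intention.
- **The .08 is not the exact threshold.** It is the effect implied by r = .20 on both paths. Under the bootstrap, power passes .94 at dr of about .07, or about .06 with the covariate; for joint significance, at about .077 or .066. This stands as a refinement. Every one of these values is well above .04.
- **The planned growth-curve SEM was not simulated.** The plan says that growth models have more power than the ANCOVA on which its estimates rest. The documents give no variance components from which a gain could be computed. The replacement figures are therefore approximate, but nothing in the plan supports a rise from .55 or .67 to above .94.
- **The plan does not claim power at .02.** It ties the phrase about small effects to dr = .04. That is so. The phrase is loose rather than a separate error, but it misleads beside a stated small benchmark of .02.
- **Mediation is exploratory.** This stands, and it limits the consequence. The plan also does not say that a null result would be read as absence of mediation.

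**Conclusion.** The concern holds. On the plan's own scale, dr = .04, r = .20 and power above .94 at N = 380 are not mutually consistent. Power under the planned test is about .55, or about .67 with a pretest covariate on the mediator. A true effect of dr = .04 would be missed in about 1 trial in 3 to nearly 1 in 2, not in fewer than 1 in 16.

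The mismatch is firm: it follows from the paragraph's own inputs and holds with or without the covariate, on one-sided alpha, and for every split of dr = .04. The replacement values are less firm, since they rest on a single-mediator regression and on an assumption about the covariate. That the two paths were both taken as correlations of .20 is an inference. No sample size or decision rule depends on the mediation power, so this should be fixed but does not threaten the trial.

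**What to change.** State the intended d, r and test for the mediation power, then correct whichever figure is wrong.

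- **(a) If dr = .04 is intended:** *With d = .20 on the mediator and r = .20, N = 380 gives power of about .55 (about .67 with a pretest covariate, r² = .25) under the bias-corrected bootstrap in a single-mediator approximation; 80% power is reached at dr of about .055 (.047 with the covariate).* If the sponsor can specify variance components for the growth-curve model, figures simulated from that model would be better.
- **(b) If r = .20 on both paths was intended:** *N = 380 gives power above .94 for dr of about .08 (d of about .41, r = .20).*

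In either case, drop the phrase that extends the claim to small effects in general, since the plan's own small value is .02. A sentence saying that a non-significant indirect effect will not be taken as evidence of no mediation would be useful but is optional.

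The cost is one or two sentences of SAP wording, and either a less favourable power (a) or a larger detectable effect (b).
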